Sponsor: PROMOMED RUS LLC, Russia	Separate study table relating to part of the dossier	(For use by national authorized bodies only)
Name of finished product: Areplivir, film-coated tablets	Volume: Pages:	
Active ingredient: Favipiravir		
Investigational medicinal product, dose and mode of administration, batch number: Investigational medicinal product: Areplivir, film coated tablets (PROMOMED RUS LLC, Russia), batch 010520 (expiry date 06.2022). Patients in Arm 1 take the investigational product Areplivir, film coated tablets: on Day 1st of treatment - 1600 mg (8 tablets) 2 times a day; on days 2-14 of treatment - 600 mg (3 tablets) 2 times a day. The drug is taken orally every 12 hours, swallowing whole tablet without chewing and washing down with a glass of water. The course of treatment is 14 days. The test drug is administered in hospital setting under supervision of a clinical investigator. The test drug is not handed over to the patient.		
Duration of the study: The total duration of the study for the patient is not more than 31 days, of which the screening period is not more than 2 days. Visits: Visit 0 (screening, not more than 2 days); Visit 1 (randomization, day 1)*; Visit 2 (day 5); Visit 3 (day 10); Visit 4 (day 15)**; Visit 5 (day 21±1)***; Visit 6 (study completion, day 28±1)***. * Visit 1 may coincide with Visit 0. ** If a patient is discharged from hospital at an earlier date, the visit will be conducted at the time of discharge (for Arm 2 patients). *** If a patient is discharged from hospital at an earlier date, then this patient does not need to visit the study site. Fatalities and serious adverse events (SAE) will be followed-up through telephone contact with the patient. Discharge of patients from a hospital is carried out in accordance with the local practice of the study site in compliance with the current sanitary and epidemiological regime.		
Efficacy criteria: The efficacy of therapy is assessed using the following endpoints: Primary efficacy criterion: 
 • Time (in days) to improvement in clinical status by categorical ordinal scale of clinical status improvement. • Rate of clinical status improvement by categorical ordinal scale of clinical status improvement by 2 or more categories at Visit 3. Secondary efficacy criteria:		

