
Certified statistical software with validated algorithms is used to perform statistical analyses and to ensure proper documenting (StatSoft Statistica 10.0., IBM SPSS Statistics 22).
 
Descriptive statistics are provided for all efficacy and safety indicators collected during the study. Continuous (quantitative) data are presented using the number of observations, arithmetic mean value, confidence interval (CI) 95% for mean, standard (rms) deviation, median, interquartile span (25th and 75th centiles), minimum and maximum.
 
Ordinal, categorical and qualitative data are presented as absolute frequencies (number of observations), relative frequencies (percent) and 95% CI (unless otherwise stated).
 
The check for normality of distribution is carried out by one of the generally accepted methods (Shapiro-Wilk test, Kolmogorov-Smirnov test). For non-Gaussian distributions, non-parametric methods will be used to compare efficacy and safety indicators.
 
Significance levels and confidence intervals are calculated as bilateral, the statistical significance of differences is two-sided by default and refers to significance level 0.05 (unless specified otherwise).
 
Analysis of demographics and other source data
 
Demographic data (age, sex) and baseline condition data are presented along with summaries in the form of absolute frequencies (number of observations), relative frequencies (percent), or using the arithmetic mean, confidence interval (CI) 95% for mean, standard deviation, median, interquartile span (25th and 75th centiles), minimum and maximum, depending on the type of variable.
 
To test the study group homogeneity hypothesis, at the baseline zero hypotheses (no differences between groups) are tested with Student's t-test (for interval measures with normal distribution in the study population), Mann-Whitney's test (for ordinary measures or for interval measures with distribution different from normal) or Fisher's exact test and χ^2 test (for qualitative indicators). If statistically significant differences between study arms are found, the magnitude of differences is estimated using confidence intervals.
 
Analysis of primary efficacy parameter
 
Primary efficacy endpoints:
 
One of the primary efficacy parameters is the time (in days) to improvement of patient's clinical status according to the categorical ordinal scale of clinical improvement.
 
 • Time (in days) to improvement in clinical status on a categorical ordinal scale of clinical improvement. 
To compare the primary efficacy indicator between arms, the Student's t-test for independent samples is used. If the necessary assumptions about the normality of distribution of this indicator are not met, the non-parametric Mann-Whitney test will be used. Also, the Kaplan-Meier technique and compilation survival tables can be used as descriptive methods for studying this efficiency parameter. Gehan-Wilcoxon test, Cox-Mentel test or Log-Rank test can be used to compare the time (in days) to improve the clinical status of the patient between the study groups.
		

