
Sponsor: PROMOMED RUS LLC, Russia	Separate study table relating to part of the dossier	(For use by national authorized bodies only)
Name of finished product: Areplivir, film-coated tablets	Volume: Pages:	
Active ingredient: Favipiravir		

The proof of the superiority hypothesis is the establishment of a statistically significant time difference (in days) before patient's clinical status improvement between the Areplivir arm and the standard therapy arm.

The next primary efficacy parameter is the percentage of patients who achieved an improvement in clinical status according to the categorical ordinal scale of clinical improvement by 2 or more categories at Visit 3.

- Rate of clinical status improvement by categorical ordinal scale of clinical status improvement by 2 or more categories at Visit 3.

For the analysis of this parameter, an intergroup comparison of percentages is used using a two-sided version of the **Fischer's exact test** (or a two-sided version of the χ^2 (chi-square) test, if all the expected values in the cells of the contingency table for this analysis are 5 or more). The percentage of patients who achieved improvement in clinical status on a categorical ordinal clinical improvement scale by 2 or more categories at Visit 3 is presented with a two-sided 95% confidence interval by treatment arm. Hypothesis testing is performed at a 5% significance level. The difference in proportion between treatment arms and the 95% bilateral confidence interval for the difference in proportion calculated by **Newcomb-Wilson technique is presented**.

The proof of the hypothesis of superiority of Areplivir film-coated tablets (PROMOMED RUS LLC, Russia) is the establishment of a statistically significant difference in the proportions of patients who achieved an improvement in clinical status according to the categorical ordinal scale of clinical improvement by 2 or more categories at Visit 3, between Areplivir arm and standard therapy arm.

Analysis of the primary efficacy parameter is performed in the ITT population (main analysis), and in the PP population (additional analysis). A summary of all efficacy indicators is provided.

Analysis of secondary efficacy parameters

The following efficacy parameters in the protocol are represented by qualitative values:

- Percentage of patients with elimination * COVID-19 according to PCR analysis at Visit 3.
- Percentage of patients transferred to intensive care unit.

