
Said statistical power (45%) is acceptable for exploratory stages of the studies aimed to select the duration for endpoint monitoring and to select the endpoint at the second (confirming) stage. In case change of the planned endpoints, separate adjustment will be made for the multiplicity of comparisons and the required number will be recalculated at the second stage.
 
Significance level used in the clinical study Significance levels and confidence intervals are calculated as bilateral, the statistical significance of differences is two-sided by default and refers to significance level 0.05 (unless specified otherwise).
 
Stopping criteria for the clinical study This protocol does not contain any statistical criteria for stopping the clinical study.
 
Accounting for missing data, data not to be analyzed and questionable data In the case of for missing data, data not to be analyzed and questionable data, appropriate statistical analysis methods are applied. Patients who will not be able to complete the course of therapy according to the protocol are included in the analysis of the main endpoint using the last observation carried forward (LOCF) method. This means that measures taken as criteria for efficacy will be assessed for such patients at the time of dropping out of the study.
 
Procedures for reporting any deviations from the original statistical plan All deviations from the final version of the statistical analysis plan will be described and substantiated in the final clinical study report.
 
Population analysis The statistical analysis includes the following patient populations:
 
 Safety population: patients who have received at least one dose of the study drug and for whom there is an assessment of condition and/or AE for at least one time point after administration. Population of all patients included in the study (Intent-to-treat, ITT): patients who received at least one dose of the drug in the study and for whom there is data for at least one visit after the baseline (Visit 0). Population of patients who completed the study as per the Protocol (Per protocol, PP): patients who have completed the study as per the Study Protocol. 
In case of developing acute respiratory distress syndrome and the need to switch patient to mechanical ventilation, the investigational drug is canceled, but the patient is not withdrawn
									

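### Time to improvement: no censoring-aware test is fixed as the deciding one, and LOCF gives no time value to patients who leave or finish unimproved

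*Combined protocol and SAP*

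**What the plan says.** All references are to the synopsis of the combined protocol and SAP.

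- **Deciding rule.** Under *Analysis of primary efficacy parameter*: "The proof of the superiority hypothesis is the establishment of a statistically significant time difference (in days") between the arms. No test is attached to this sentence.
- **Test in firm wording.** Under the same heading, the t-test is prescribed, with Mann-Whitney as the fallback: "for independent samples is used. If the necessary assumptions about the normality of distribution of this indicator are not met, the non-parametric".
- **Optional methods.** Kaplan-Meier and survival tables are allowed as descriptive tools. Gehan-Wilcoxon, Cox-Mantel or log-rank "can be used to compare the time (in days) to improve the clinical status of the patient between the study groups". Nothing says when they apply or whether they would decide.
- **Missing data.** Under *Accounting for missing data*, patients unable to complete the course of therapy "are included in the analysis of the main endpoint using the last observation carried forward (LOCF) method". The explanation is: "This means that measures taken as criteria for efficacy will be assessed for such patients at the time of dropping out of the study".
- **ITT set.** Under *Population analysis*, a patient needs at least one dose, and "there is data for at least one visit after the baseline (Visit 0") is required.
- **Follow-up.** The last visit is Visit 6, day 28±1. For Visits 5 and 6: "If a patient is discharged from hospital at an earlier date, then this patient does not need to visit the study site". Ventilated patients are not withdrawn and are followed to Visit 6.

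The synopsis gives no censoring rule. It gives no time value for a patient who leaves, dies or reaches day 28 unimproved. It also does not state the size of improvement that counts as the event: two or more categories is written only for the Visit 3 endpoint.

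**The concern.** A t-test or Mann-Whitney test needs a number of days for every patient. A patient who has not improved does not have one. LOCF answers a different question, namely what the status was when last seen. To turn that into days, the analyst must either use the exit day as the time, or carry the patient to day 28 as not improved. The first makes the time too short, and the second may make it too long. The plan does not choose.

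This can affect a claim of superiority only if losses differ between the arms. The design makes that possible: the study is open-label, and Visit 4 is brought forward to discharge for Arm 2 patients only. The documents give no loss rates, so none can be asserted.

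**Working it through.** **1. The plan's own figure.** No power is stated for time to improvement. The sample size concerns the Visit 3 response rate: 65% against 80%, 107 per arm, unpooled Z test, alpha 0.05 in one direction.

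Power = Φ(0.15 / √[(0.65×0.35 + 0.80×0.20)/107] − 1.645) = Φ(0.15/0.0602 − 1.645) = Φ(0.848) = 0.802.

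This matches the stated 0.80170, but it says nothing about the time endpoint. It supplies only the day-10 rates used below.

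**2. How many patients lack an improvement time?** Assume a constant hazard. The share unimproved at day t is then (1 − p)^(t/10), with p improved by day 10.

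| Day | p = 65% | p = 80% |
|---|---|---|
| 10 | 35% | 20% |
| 15 | 0.35^1.5 = 21% | 0.20^1.5 = 9% |
| 28 | 0.35^2.8 = 5.3% | 0.20^2.8 = 1.1% |

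Few patients followed to day 28 would lack a time. Patients who leave early are the larger issue.

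**3. Simulation under no drug effect.** From the documents: 100 per arm, two-sided 0.05 (2.5% per side), last visit at day 28. Assumed: exponential times rounded to whole days, 65% or 72.5% improved by day 10 in both arms (72.5% is the midpoint of 65% and 80%), and the loss rates and windows. Mann-Whitney test, 20,000 trials per cell in the main runs.

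*Losses unrelated to outcome, 10% against 0%:*

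| Coding | Wrong result for the arm with more losses | Days 2-14 | All windows tried (days 2-8, 2-14, 5-8) |
|---|---|---|---|
| Exit day | false win | about 5% | 4.5-7.2% |
| Carried to day 28 | false loss | about 4.5% | 4.0-6.3% |

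A log-rank test that censors these patients stays at 2.4-2.8% each way. If the ITT rule removes exits before Visit 2 (day 5), the all-window ranges fall to 3.9-5.5% and 2.5-4.9%. If Visit 1 counts as a visit after Visit 0, nothing is removed.

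*Failures who leave unimproved and are scored at the exit day, 10% against 0%:*

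| Exit window | Result for the arm with more failures |
|---|---|
| Within days 2-8 | false wins 3.4-8.4%, highest when all leave on days 2-5 |
| Days 2-14 | false wins about 1.5-2.5%, not above nominal |
| Days 8-14 | false losses about 6-8% |

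With the ITT removal, the first row falls to 2.3-4.9%. At 10% against 10%, early exits give 2.1-2.5%, so there is no inflation.

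**4. Why the direction turns.** In a rank test, a score before the median improvement time helps the arm and a later one hurts it. The median is 10 × ln 2 / −ln(1 − p):

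- p = 65%: 6.93/1.050 = 6.6 days
- p = 72.5%: 6.93/1.291 = 5.4 days

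The mean exit day is 5 for days 2-8, 8 for days 2-14 and 11 for days 8-14. Only the first lies below both medians. Losses unrelated to outcome behave differently: the exit day always shortens the true time, and day 28 never shortens it.

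**5. Power of the candidate tests** (100 per arm, two-sided 0.05, no losses, non-improvers placed at day 28):

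| Scenario (assumed) | Log-rank | Gehan-Wilcoxon | Mann-Whitney |
|---|---|---|---|
| Proportional hazards, 65% vs 80% by day 10 | 84% | 74% | 74% |
| Purely early effect (hazard ratio 1.75 to day 7, curves equal by day 28) | 47% | 76% | 76% |

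**The case against.** **What stands.** Mann-Whitney is a valid test if everyone shares a day-28 horizon and non-improvers are ranked last, and also if losses are equal. Bias needs unequal losses, for which the documents give no rate. LOCF in its ordinary sense leaves an unimproved patient unimproved, so the exit-day coding is one possible reading and not what the text plainly says. The document supplied is a synopsis that refers to a final SAP, and that SAP may settle the coding.

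**Stronger readings that the documents do not support:**

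- *That the plan requires a test that ignores censoring.* The same paragraph permits three censoring-aware tests. The gap is that none is fixed as deciding.
- *That exit-day coding always favours the arm with more exits.* For failures this holds only for early exits. Spread over the 14-day course it disappears, and later it reverses.
- *That ventilated patients are cut off by LOCF.* A specific rule, repeated several times, keeps them in the study and in the ITT data to Visit 6. At most a cross-reference is missing.
- *That unimproved completers would be left out, at a large cost in power.* They meet the ITT definition, and ITT is the main analysis. What is missing is their time value.
- *That the best of several tests will be picked.* The plan leaves the choice open but does not say this.

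**What does not answer the point.** Permission to use log-rank does not say that it decides. Neither the common horizon nor the ranking of non-improvers is written down.

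**Conclusion.** The point holds in a limited form and should be fixed. For a primary endpoint that can by itself count as proof of superiority, the synopsis leaves the deciding test open. Its firmly worded tests take no censoring indicator, and its LOCF rule supplies no event time.

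The size is moderate and conditional. With 10% against 0% losses unrelated to outcome over days 2-14, the error on one side is about 5% or about 4.5% instead of 2.5%, in opposite directions under the two codings. For failures scored at the exit day, both size and direction depend on when they leave. All loss rates, exit windows and the exponential shape are assumptions. With equal losses none of this bias arises.

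Confidence is high that the synopsis does not state the rule. It cannot extend to the final SAP, which was not supplied.

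**What to change.** Before the stage 2 analysis:

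1. Name one deciding two-sided censoring-aware test from those already listed: log-rank with Kaplan-Meier curves, or Gehan-Wilcoxon if an early effect is expected. Keep the t-test and Mann-Whitney as sensitivity analyses.
2. Replace LOCF for this endpoint. Count deaths, and patients followed to day 28 without improvement, as not improved at day 28. Censor true losses at their last status assessment. Cross-refer to the existing rule that ventilated patients stay in follow-up to Visit 6.
3. State the size of improvement on the ordinal scale that counts as the event.
4. The synopsis already describes an interim report on 80 patients. If the change is made after those stage 1 data were seen, report it as such.
5. If the final SAP already sets a rule, make the two texts agree.

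The cost is SAP wording, with no new data. The trade-off is power: log-rank falls to 47% against 76% for Mann-Whitney under the purely early effect simulated. Gehan-Wilcoxon matched Mann-Whitney in both scenarios but gives up about 10 points to log-rank under proportional hazards (74% against 84%).

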
Statistical methods:
 
Justification of sample size
 
The study will randomize 200 patients. Given the possible non-inclusion of patients at the screening stage, the maximum number of patients to sign the Informed Consent Form in the Patient Information Leaflet and to participate in screening will be no more than 210 people.
 
At the first stage, 40 patients are included in each study arm and the most sensitive efficacy criterion of the two selected is determined, or additional analysis is carried out to select the criterion from secondary ones. Given 40 patients in each of the study arms, the sensitivity of the study to confirm 15% superiority by incidence, supposing the expected response 80% in the test drug arm, will exceed 45%.
 
Two Independent Proportions (Null Case) Power
 
Analysis
 
Numeric Results of Tests Based on the Difference: P1 - P2 H0: P1 - P2 ≥ 0. H1: P1 - P2 = D1 < 0. Test Statistic: Z test with pooled variance
 
  
 	Sample Size Grp 1	Sample Size Grp 2	Prop H1 Grp 1 or Trtmnt P1	Prop Grp 2 or Control P2	Diff if H0 D0	Diff if H1 D1	Target Alpha	Actu Alpha	
   
 Power	0.4553	40	40	0.6500	0.8000	0.0000	-0.1500	0.0500	0.0500	
  
				Sample Size Grp 1	Sample Size Grp 2	Prop H1 Grp 1 or Trtmnt P1	Prop Grp 2 or Control P2	Diff if H0 D0	Diff if H1 D1	Target Alpha	Actu Alpha	Power	0.4553	40	40	0.6500	0.8000	0.0000	-0.1500	0.0500	0.0500
	Sample Size Grp 1	Sample Size Grp 2	Prop H1 Grp 1 or Trtmnt P1	Prop Grp 2 or Control P2	Diff if H0 D0	Diff if H1 D1	Target Alpha	Actu Alpha													
Power	0.4553	40	40	0.6500	0.8000	0.0000	-0.1500	0.0500	0.0500												

Sponsor: PROMOMED RUS LLC, Russia	Separate study table relating to part of the dossier	(For use by national authorized bodies only)
Name of finished product: Areplivir, film-coated tablets	Volume: Pages:	
Active ingredient: Favipiravir		

Said statistical power (45%) is acceptable for exploratory stages of the studies aimed to select the duration for endpoint monitoring and to select the endpoint at the second (confirming) stage.

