In case change of the planned endpoints, separate adjustment will be made for the multiplicity of comparisons and the required number will be recalculated at the second stage.

The total planned number of patients before the completion of the first stage will be 100 patients in each of the arms.

The estimated calculation until the data of the first stage are obtained is as follows. Given the available data from Chinese researchers, 15% superiority of favipiravir therapy over standard therapy without favipiravir is allowed in relation to the rate of improvement by 2 or more categories on categorical scale by day 10 of treatment. The adopted higher response to standard therapy of 70% is associated with a longer duration relative to the Chinese study (10 days instead of 7 days).

An RCT enrolling patients within 12 days of symptom onset found that favipiravir was superior to arbidol in terms of the clinical recovery rate at day 7 in patients with mild illness (62 [56%] of 111 with arbidol vs 70 [71%] of 98 with favipiravir), but not in those with critical illness (0 vs 1 [6%]). (Chen C. Huang J. Cheng Z. et al. Favipiravir versus arbidol for COVID-19: a randomized clinical trial. medRxiv. 2020; (published online April 15.) (preprint).

Tests for Two Proportions

Numeric Results for Testing Two Proportions using the Z-Test with Unpooled Variance

H0: $P_1 - P_2 \geq 0$ vs. H1: $P_1 - P_2 = D_1 < 0$.

Target	Actual	Diff						
Power	Power*	N1	N2	N	P1	P2	D1	Alpha
0.80170	107	107	214	0.6500	0.8000	-0.1500	0.0500	0.80

* Power was computed using the normal approximation method.

Thus, the minimum number of subjects required for a clinical study is 200 with 100 subjects randomized to each of the two groups.

Statistical analysis

The purpose of statistical analysis is to prove superiority of Areplivir, film-coated tablets (PROMOMED RUS LLC, Russia), over standard therapy in patients hospitalized with COVID-19.

The results of statistical analysis, descriptive statistics and illustrative tables, graphs, lists will be presented in interim and final clinical study reports.

General methods of analysis

Statistical analysis is carried out in accordance with the requirements of the Guideline for Good Clinical Practice (ICH 9) approved by the Eurasian Economic Commission, and other applicable requirements and laws.

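### Each of two primary endpoints is separately called proof of superiority at two-sided 5% with no joint rule; if either suffices, false claims for Areplivir run at 3.5-4.5% instead of 2.5%

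*Combined protocol and SAP*

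**What the plan says.** All references are to the combined protocol and SAP, section 2, Overview (Synopsis).

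- **Two proof statements.** Under *Analysis of primary efficacy parameter*, the text for time to improvement reads "The proof of the superiority hypothesis is the establishment of a statistically significant time difference (in days) before patient's clinical status improvement". For the proportion improved by 2 or more categories at Visit 3, the proof of superiority "is the establishment of a statistically significant difference in the proportions of patients who achieved an improvement in clinical status".
- **Level.** For the rate, "Hypothesis testing is performed at a 5% significance level". For time, the default under *General methods of analysis* applies: "the statistical significance of differences is two-sided by default and refers to significance level 0.05". *Significance level used in the clinical study* repeats that default.
- **Test for time.** The t-test comes first, with Mann-Whitney if normality fails. Three further tests (Gehan-Wilcoxon, Cox-Mantel, log-rank) "can be used to compare the time (in days) to improve the clinical status of the patient between the study groups".
- **Selection at stage 1.** Under *Justification of sample size*, after 40 patients per arm "the most sensitive efficacy criterion of the two selected is determined, or additional analysis is carried out to select the criterion from secondary ones". Low power is accepted there as suited to "exploratory stages of the studies aimed to select the duration for endpoint monitoring and to select the endpoint at the second (confirming) stage".
- **Multiplicity.** The only sentence, given there and again under *Interim analysis*, is "In case change of the planned endpoints, separate adjustment will be made for the multiplicity of comparisons". It names no method.

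The text does not say whether one or both endpoints must succeed, what makes a criterion the most sensitive, or whether the 80 stage 1 patients enter the confirmatory test.

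**The concern.** The stated purpose of the analysis is to prove superiority in a phase III trial. Two tests, each at the full 5% and each called proof, give two chances of a false claim unless something joins them. The multiplicity sentence does not: keeping both planned primaries is not a change of endpoints, and whether picking one of the two counts as a change is unclear.

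Timing adds to this. The study is open-label, and the synopsis already belongs to an interim report on 80 patients. A success rule, or a choice of test, written after that report could be shaped by the results.

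**Working it through.** **Inputs from the synopsis.** Two-sided alpha 0.05 per endpoint (critical value 1.96); 40 per arm at stage 1 and 100 per arm in total, so an information fraction of 40/100 = 0.4 if pooled; rates 65% vs 80% in the sizing tables; a 70% control response in the text, which with the 15-point difference gives 70% vs 85%.

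**Assumption.** The documents give no correlation ρ between the two test statistics. I show 0, 0.5, 0.7, 0.8 and 0.9. A null simulation reading both endpoints from the same improvement process (65-80% improved by day 10, 100 per arm) gave 0.70-0.83. It would be lower if time uses a different improvement threshold from the 2 categories used for the rate; the synopsis states no threshold for time.

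**The plan's own figures.** It states no overall type I error. Its sizing figures reproduce: power 0.4553 at 40 per arm by exact enumeration of the one-sided pooled Z test, and 0.8017 at 107 per arm by the one-sided unpooled normal approximation.

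**A. Either endpoint suffices.** With (Z1, Z2) bivariate normal under the global null, positive values favouring Areplivir:
- two-sided error = 1 − P(|Z1| ≤ 1.96 and |Z2| ≤ 1.96)
- false claims for Areplivir = 1 − P(Z1 ≤ 1.96 and Z2 ≤ 1.96)

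**B. Stage 1 picks one, all 200 pooled.** The final statistic is √0.4·(stage 1 Z) + √0.6·(stage 2 Z) for the picked endpoint, integrated over the stage 1 result. B1 picks the more favourable endpoint; B2 picks the larger absolute statistic, the worst case for two-sided error.

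| ρ | A, two-sided | A, for Areplivir | B1, for Areplivir | B2, two-sided |
|---|---|---|---|---|
| 0 | 9.75% | 4.9% | 4.4% | 7.7% |
| 0.5 | 9.1% | 4.5% | 3.9% | 7.3% |
| 0.7 | 8.35% | 4.2% | 3.6% | 6.9% |
| 0.8 | 7.8% | 3.9% | 3.4% | 6.6% |
| 0.9 | 7.0% | 3.5% | 3.2% | 6.1% |

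The targets are 5% two-sided and 2.5% in favour of Areplivir. Under B1 the two-sided error stays at 5.0%: the excess in one direction is offset in the other.

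**C. Both endpoints required.** Two-sided error = 0.05 + 0.05 − A: 0.10 − 0.0907 = 0.9% at ρ = 0.5 and 0.10 − 0.0704 = 3.0% at ρ = 0.9. No inflation.

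**D. Picked endpoint, post-stage-1 patients only.** These data are independent of the selection, so the error is 5.0%.

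**Effect of Holm.** Rejecting the smaller p-value at 0.025 gives a family-wise error of 4.7%, 4.3%, 4.0% and 3.6% at ρ = 0.5, 0.7, 0.8 and 0.9.

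**Power for the rate, pooled Z, 100 per arm.** Power = Φ[(0.15 − z·SE0)/SE1], where SE0 is the pooled (null) and SE1 the unpooled (alternative) standard error. At two-sided 0.05 and 0.025:
- 65% vs 80%: 66.3% and 55.4%
- 70% vs 85%: 72.2% and 61.9%

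The second figure is Holm's floor, when time never helps. With equal standardised effects on both endpoints (an assumption), Holm's power for the rate is 61.0-59.8% (65% vs 80%) and 67.5-66.3% (70% vs 85%) for ρ = 0.5-0.9.

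**The case against.** The strongest objection is that this is a synopsis. *Procedures for reporting any deviations from the original statistical plan* refers to a final version of the statistical analysis plan, where a success rule, a definition of sensitivity and the use of stage 1 patients would normally sit. That stands as a limit on confidence. It does not undo two proof statements that, as printed, each suffice.

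Second, the text nowhere says that either endpoint suffices. That is so, but it also never says both are needed, and each statement is complete in itself.

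Third, stage 1 is called exploratory and stage 2 confirming, which fits testing later patients only as well as it fits pooling. This stands. A reader might infer from the total of 200 that the 80 patients are reused after choosing the endpoint; the documents do not say so, and the B figures are conditional on it.

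Fourth, a reader might take 6.1-7.3% as the effect of selection. That needs selection by larger absolute statistic, including results against Areplivir. Selection by the more favourable result leaves two-sided error at 5.0% and shows only as 3.2-3.9% against 2.5% in Areplivir's favour.

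Fifth, a reader might object that choosing a secondary endpoint is uncontrolled. The multiplicity sentence does promise an adjustment there, though without a method.

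Finally, the test for time is not wholly open: t-test, then Mann-Whitney, comes first, and only the survival tests are optional.

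**Conclusion.** The point holds as a stated decision rule that does not secure its stated level. Applied as printed, with either result sufficient, false claims for Areplivir run at 3.5-4.5% instead of 2.5%, and two-sided error at 7.0-9.1% instead of 5%. This assumes a correlation of 0.9-0.5 and approximate normality of the two statistics; 9.75% at zero correlation is the two-sided ceiling over the correlations shown. The inflation is modest, but it bears on the trial's main claim.

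The documents do not support the stronger inference that error is inflated on every reading: requiring both endpoints, or confirming on post-stage-1 patients only, inflates nothing. Confidence is moderate because a fuller SAP may exist. It should be settled before the final analysis.

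**What to change.** State one success rule in the SAP.

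- **If both primaries are kept:** control family-wise error at two-sided 0.05 by Holm or Hochberg, with one p-value per endpoint. For time, use the test the synopsis puts first (t-test, or Mann-Whitney if normality fails). Use another test only if its choice is documented as made without the stage 1 results. Treat the optional survival tests as supportive.
- **If stage 1 selection is kept:** define the selection criterion, and either confirm on post-stage-1 patients only or use a closed combination of stage-wise p-values covering every candidate endpoint.

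**Cost.** Holm or Hochberg needs SAP wording and no new data. With Holm at 100 per arm, power for the rate falls from 66% to 55-61% (65% vs 80%) or from 72% to 62-68% (70% vs 85%).

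Confirming on the remaining 100 − 40 = 60 per arm gives 45% or 50% power for the rate. Reaching 80% would need about 138 or 121 per arm in stage 2, and the synopsis provides for recalculating the number only if the planned endpoints change.

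Power does not settle the choice between Holm and a closed combination test. The order depends on the stage 1 intersection test and the correlation. With Simes at stage 1, equal effects and 65% vs 80%, power for the picked endpoint and Holm's power for at least one endpoint are about level at correlation 0.8 (65.6% and 65.7%); at 0.9 the combination test is ahead (about 65% against 63%).

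If a fuller SAP already holds the rule, a reference to it closes the point.
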